to a post-DVT activity regimen in children. I propose a validated, fitness tracker, the Fitbit, to improve adherence to a 16-week activity regimen in a pilot randomized controlled trial (RCT), in which 44 subjects with DVT will be assigned to the intervention group or to a comparison group. The primary outcomes will consist of a) feasibility indicators determined *a priori* (eligibility, consent, adherence, retention) and b) estimates of effect size associated with the prescribed activity regimen, by describing within-subject change in QoL and 'potential' biomarkers of PTS pre and post intervention in each group.

STUDY DESIGN (Figure 2)

The study design is that of a pilot RCT to test the feasibility of the proposed activity tracker to increase activity in children post DVT, against standard practice, which currently consists of providing education about PTS and instructions to 'be active'. I will use a validated activity tracker, the Fitbit and its data platform- the Fitabase.

METHODS

I. STUDY SETTING

All newly diagnosed patients with first, lower extremity DVT diagnosed at Children's Health System of Texas (CHST) or referred to the Hemostasis Thrombosis Center (HTC) at CHST who have completed 12 weeks (± 2 weeks) of anticoagulation therapy, will be approached for recruitment.

II. ELIGIBILITY CRITERIA

Parents must provide written, informed consent before any study procedures occur.

INCLUSION CRITERIA	RATIONALE
1. Age 7-21 years	VTE is seen across all age groups
2. A radiologically confirmed, acute, proximal (iliofemoral and femoropopliteal) first lower extremity DVT and/or confirmed,	Population with proximal DVT and/or PE deemed to be at highest risk of PTS

acute pulmonary embolism (unilateral or bilateral)	
3. 12 weeks (± 2 weeks) after starting anticoagulation	To mitigate the small theoretical risk of clot dislodgement with activity soon after DVT diagnosis
4. Out-patient ambulatory status	Protocol involves increasing activity

EXCLUSION CRITERIA	
1. Contraindication to increasing activity such as patients with juvenile arthritis, poor balance, congestive heart failure etc.	Protocol involves increasing activity

III. STUDY PROTOCOL

The study has 3-4 planned visits, which will coincide with the standard of care visits.

Screening

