- b. Subjects who need to continue long term prophylactic anticoagulation will still be eligible and will be included at discretion of their attending hematologist.
- c. The activity tracker, the Fitbit, is made up of a flexible durable material used in many sports watches (and one that does not contain latex) with a surgical grade stainless steel clasp and contains traces of nickel. It is meant to be worn day and night on the wrist. Because there's a possibility of skin irritation and allergies with any type of jewelry, all participants in this study will be warned and care and wearing tips will be provided. They will be monitored for any skin problems during the clinic visits and a treatment plan will be made in collaboration with their primary pediatrician should any skin irritation develop. I will ask to be notified immediately of any such occurrence at home and will then contact the participant or the family to assess

their clinical condition and make a treatment plan based on the severity of the skin condition.

VII. OUTCOMES AND POWER CALCULATIONS

Primary Outcomes will be 1) **feasibility indicators (Table 2)** measured throughout trial. The level of adherence in the intervention group will be calculated as the proportion meeting the weekly steps/day goal during the 'active' 8-week period of the total 16 weeks of intervention as determined by the Fitabase data platform output, and 2) **change in clinical outcomes**

such as PTS biomarkers at baseline and Visit 2, and QoL (at all visits). Secondary outcome: I will assess for PTS with validated scales at the 6 and 9 month follow-up visit as is standard of care.

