Analyses: The objectives of this trial are to assess the feasibility of the design and to measure the effect size of the intervention. All analyses will therefore be descriptive and will be performed once, at the end of the trial. Means and standard deviations, or when appropriate, medians and semi-inter-quartile ranges will be used to describe demographic and clinical characteristics. Reasons for non-eligibility, lack of consent, dropout and lack of compliance will be documented. For feasibility indicators, we (study investigators and [name]-biostatistician) will describe rate of eligibility (proportion of subjects screened who fully meet trial eligibility criteria to participate in the trial), rate of consent (the proportion of eligible subjects who consent to participate) and rate of loss to follow-up (proportion of randomized subjects who drop out of the trial, in total, and by allocated intervention). We will also describe the level of compliance in the intervention group, calculated as the ratio of who complied with the activity prescription to the number given the prescription. We will consider the trial *successful* if the following criteria are met: rate of eligibility $\geq 30\%$, rate of consent $\geq 30\%$, rate of loss of follow-up $<20\%$, level of compliance $\geq 60\%$ and proportion of subjects who complete the trial $\geq 80\%$. For the clinical outcomes (including the secondary outcomes), we will describe change (means and standard deviations) in the intervention and control groups, from baseline to 6 month, in the QoL scores and PTS biomarkers. Each change score will be interpreted for clinical significance and common responses counted for frequency of occurrence. The impact of the activity

Table 2: Feasibility Indicators

Proportion of screened subjects who meet eligibility criteria: $\geq 30\%$

Proportion of screened subjects who provide consent: $\geq 30\%$

Level of adherence in the intervention arm: $\geq 60\%$

Proportion of subjects who complete the trial: $\geq 80\%$

tracker to promote continued physical activity in the last 2 weeks of the 12-week period would be explored. We will also assess the impact of covariates such as age, sex, BMI, baseline activity, intensity of activity over and above the activity prescription, on change scores.

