Sample size calculation: For reasons of practicality and cost, we have decided to limit the size of this pilot RCT to 44 subjects (20 in each arm; 22 after considering a 20% drop out rate). We anticipate that the probable primary outcome for the larger trial will be change in rate of PTS development and/or progression. This trial may also provide compelling preliminary data for future studies. For example, if this intervention reduces the risk of PTS from 26% (known probability of PTS) to 10%, this pilot study has 71% chance of showing a promising trend (p-value<0.2) that the intervention reduces the risk of PTS. We acknowledge that the small size of this pilot study limits the validity of the findings; therefore, we will be cautious with such analyses.

I. RECRUITMENT

- a. Information about the clinical study will be provided via direct communication by study investigators and physicians at Children's Medical Center including ED physicians, hospitalists, and general pediatricians attending on the inpatient medicine services and outpatient continuity clinic as well as house officers.
- b. Information regarding the study will be available on the University of Texas Southwestern clinical trials website and at clinicaltrials.gov.
- c. Potential subjects will be identified through review of new patient referrals to Children's Medical Center, inpatient admissions and/or consultations for thrombosis.
- d. Each subject will receive financial compensation for participation. Payment will be made at completion of the study visits at Visits 1 and 2 (\$25 each) and at the end of Visit 3 (\$50) based on attendance and return of the tracking logs.
- e. Expected recruitment rate will be 2-3 participants per month.
- f. Duration of recruitment period is expected to be approximately 24 months.

- g. Assessment of study recruitment and retention will be performed when 20 participants have been enrolled on the study, or at approximately 9 -12 months.

II. DATA COLLECTION, MANAGEMENT AND ANALYSIS

a. DATA COLLECTION METHODS

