using mean (standard deviations [SD]) for continuous outcomes, and raw counts (%) for categorical outcomes are reported. For the clinical end points, using an intent-to-treat analysis that includes all participants with data at baseline and 6 months (end of the intervention period), within-patient change from baseline (diagnosis or pre-VTE levels) to 6 months (mean, SD) in the physical activity will be compared to standard care in the following measures: D-dimer, FVIII, CRP, thrombin generation assay parameters of endogenous thrombin potential and peak thrombin, fibrinolysis on thromboelastography, QoL (total and physical), selfreported physical activity levels, and PTS (change from 6 to 9 months). This will be averaged for each group, and within-group differences will be compared between the standard care and physical activity groups using a t test. ECS use will be descriptively described but not included in a formal analysis.

ETHICS AND DISSEMINATION

I. RESEARCH ETHICS APPROVAL

This protocol and template informed consent forms will be reviewed and approved UT Southwestern IRB with respect to scientific content and compliance with applicable research and human subjects regulations. Subsequent to initial review and approval, the investigators will submit progress reports to the IRB at least annually and at study closure.

II. PROTOCOL AMMENDMENTS

Any modifications to the protocol, which impact the conduct of the study, or potential risk/benefit of the participants, will require a formal amendment to the protocol with IRB approval.

III. CONSENT OR ASSENT

Informed consent will be obtained after information has been provided to patients' families along with a discussion of the risks and benefits along with opportunity for questions. Consent forms will be provided for all parents involved in the trial.

IV. CONFIDENTIALITY

Records of each patient's participation in this study, including the original informed consent document, will be kept in a locked file cabinet in the Center for Cancer and Blood Disorders at Children's Medical Center. Access to local

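### The plan calls its analyses descriptive, then specifies unadjusted between-arm t tests of change on ten measures, and commits nowhere to a between-arm estimate with its uncertainty

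*Combined protocol and SAP*

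**What the plan says.** Three places describe how the clinical outcomes will be handled.

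- **Primary Aim.** The second part of the primary outcome is "estimates of effect size associated with the prescribed activity regimen, by describing within-subject change in QoL" and candidate biomarkers, before and after the intervention in each group.
- **VII. Outcomes and Power Calculations, Analyses.** The objectives are feasibility and measuring the size of the intervention effect. From this the plan concludes: "All analyses will therefore be descriptive and will be performed once, at the end of the trial". For QoL and biomarkers it promises the mean and SD of change in each arm from baseline to 6 months. Trial success is defined by feasibility criteria only.
- **II.c Statistical Analyses.** Within-patient change is averaged by arm, and "within-group differences will be compared between the standard care and physical activity groups using a t test". The list begins "D-dimer, FVIII, CRP, thrombin generation assay parameters of endogenous thrombin potential and peak thrombin". It continues with fibrinolysis on thromboelastography, QoL total, QoL physical, self-reported activity, and PTS change between 6 and 9 months, which makes ten measures. No alpha, sidedness, multiplicity rule or reporting rule accompanies the tests.

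Biomarkers and QoL stand under Primary Outcomes in section VII, so most of the tested measures are not peripheral. The only p-value threshold in the document is in the sample size paragraph, which illustrates the chance of "showing a promising trend (p-value<0.2) that the intervention reduces the risk of PTS".

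**The concern.** A between-arm t test is an inferential procedure, so the two sections cannot both be followed. Section II.c itself separates the two ideas: it says stocking use will only be described and kept out of formal analysis, which implies that the ten listed measures do get a formal analysis.

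Two things are at stake. First, ten p-values from a 44-subject pilot, with no rule on how to read them, leave room for a chance result to attract attention. Second, the stated objective is to measure an effect size. In a randomized trial that means the between-arm difference and its precision. The plan promises arm-level summaries in one section and a test in the other, but never the interval. A next trial would plan from the interval and the SD.

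**Working it through.** **The plan's own figure.** The sample size paragraph gives a 71% chance of p<0.2 if PTS risk falls from 26% to 10%. With 22 per arm, a one-sided 0.2 level and the pooled normal approximation:

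- null SE = √(2 × 0.18 × 0.82 / 22) = 0.1158
- alternative SE = √((0.26 × 0.74 + 0.10 × 0.90) / 22) = 0.1133
- power = Φ((0.16 − 0.8416 × 0.1158) / 0.1133) = Φ(0.552) = 70.9%

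The figure reproduces one-sided. Two-sided it would be 54.1% at 22 per arm and 51.4% at 20 per arm. It concerns a comparison of PTS risk. Section II.c names no test of PTS risk; it lists PTS only as a 6-to-9-month change.

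**Chance of a false-positive result among the ten t tests.** The number of tests (10) comes from section II.c. The level of 0.05 is an assumption.

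- Independent outcomes: 1 − 0.95^10 = 0.401. Expected number of false positives: 10 × 0.05 = 0.5.
- Equally correlated outcomes (simulation of ten two-sided z tests, 200,000 draws):

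| Assumed correlation between outcomes | P(at least one p<0.05) |
|---|---|
| 0 | 40% |
| 0.3 | 35% |
| 0.5 | 29% |
| 0.7 | 21% |

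Independence is an upper reference here. Two of the measures come from the same thrombin generation assay, and 8 of the 23 items in the PedsQL total score are the physical items.

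**Precision of the unadjusted contrast.** With 20 per arm (the plan's number after dropout), the 95% CI half-width for a difference in mean change is t(0.975, 38 df) × √(2/20) = 2.024 × 0.316 = 0.64 SD of change. With 22 per arm it is 2.018 × √(2/22) = 0.61 SD.

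**Gain from adjusting for baseline.** Let σ² be the outcome variance, taken as equal at both visits, and ρ the correlation between Visit 1 and 6 months. This is not the between-outcome correlation in the table.

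- Variance per subject for a change score: 2σ²(1 − ρ)
- Variance per subject for ANCOVA: σ²(1 − ρ²)
- Ratio: (1 + ρ)/2

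At ρ = 0.3 the ratio is 0.65, a 35% reduction. At ρ = 0.7 it is 0.85, a 15% reduction. The half-width of 0.64 SD of change becomes 0.64 × √0.65 = 0.52 or 0.64 × √0.85 = 0.59, ignoring the one degree of freedom spent. The documents give no value of ρ, so the range is an assumption.

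**PTS.** The schedule (Table 1) has PTS assessment at Visits 2 and 3 only, so there is no pre-randomization value to adjust for. A 6-to-9-month change also leaves out any difference that arose before Visit 2, during the 16-week intervention. At the plan's own rates and 20 per arm, the approximate 95% half-width for a risk difference is 1.96 × √((0.1924 + 0.09)/20) = 0.23.

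**The case against.** The strongest case on the other side has four parts.

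1. **Nothing depends on these p-values.** Success rests on feasibility criteria alone, the size was set for practicality and cost, and the sample size paragraph promises caution because the trial is small. This stands and limits the harm. It does not remove the t tests, and the caution comes with no rule for applying it.
2. **The effect can be recovered.** Mean and SD of change per arm, with the arm sizes, give the unadjusted difference and its interval. A reader might infer that the plan withholds all between-arm information; it does not. What is missing is the commitment to report the interval, and a baseline-adjusted estimate, which arm-level summaries of change cannot supply.
3. **p<0.2 does not govern the t tests.** A reader might carry the promising-trend threshold over to all ten measures, obtain 1 − 0.80^10 = 89%, and conclude that false signals are likely. The documents do not support this. The threshold appears once, in an example about PTS risk, and no section applies it to the tests in II.c.
4. **Deleting every p-value is a preference.** This also stands. Tests that are labelled exploratory, reported in full and accompanied by intervals would resolve the conflict too.

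**Conclusion.** The contradiction is real and sits in the current text: descriptive analysis only in section VII, between-arm t tests on ten measures in section II.c. The missing commitment to a between-arm estimate with its uncertainty matters more than the p-values, because measuring the effect size is a stated objective.

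The multiplicity risk is material but below one half: 40% under independence and about 35% to 21% at assumed correlations of 0.3 to 0.7, all at an assumed level of 0.05. The documents do not say that a small p-value would be called a signal, so it would be too strong to conclude that false claims are likely. The precision gain from baseline adjustment, about 35% to 15% in variance, rests on an assumed baseline to follow-up correlation of 0.3 to 0.7 and equal variances at the two visits. The point affects how clinical results are reported and used for planning. It does not affect the feasibility conclusion.

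**What to change.** Reconcile section VII (Analyses) with section II.c as follows.

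- For each biomarker, QoL and activity measure with a Visit 1 value, replace the t test on change with the between-arm mean difference at 6 months adjusted for the Visit 1 value (ANCOVA), reported with its 95% CI and the SD. Name Visit 1 as the baseline, since II.c currently describes baseline as the level at diagnosis or before the VTE.
- For PTS, report the between-arm risk difference with a 95% CI at 6 and at 9 months, without baseline adjustment.
- Report all ten outcomes whatever the result, label any retained p-values exploratory, and state that no significance claims will be made.
- In the sample size paragraph, either remove the p<0.2 example or state its test and sidedness.

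The cost is protocol wording and slightly more analysis work. No extra subjects, visits or samples are needed, because the Visit 1 measurements are already scheduled. The downside is that the intervals will be visibly wide, which is an accurate picture of what 20 per arm can show.

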mechanisms to remove thrombus, which are often impaired in children with DVT[27]. Even in those who achieve clot lysis, permanent damage to venous valves occurs frequently, likely via thrombus-induced activation of inflammation[14]. *I propose that a bidirectional relationship between inflammation and abnormal fibrinolysis drives a feedback loop resulting in increased complications after DVT over time, including PTS (Figure 1).*

Bringing together this insight and our current knowledge of coagulation assessment by global assays -focusing on PTS- may uncover new and better approaches to identify and treat at-risk individuals. Exercise has shown to decrease thrombin generation and fibrinolytic markers in children as well as adults. Alterations in the level of related biomarkers, reflecting coagulation activation, inflammation and markers of fibrinolysis, may be of interest when assessing a patient's risk of developing PTS.

Extrapolating from the above, I propose that an activity regimen for children after lower extremity DVT is unlikely to be harmful, maybe of benefit and needs further study. In the past, investigator initiated trials involving prevention or treatment of pediatric VTE have been terminated because of feasibility concerns[28]. Accordingly, a pilot study to establish feasibility of this approach is required before proceeding to a fully powered, definitive trial.

INNOVATION

This proposal is innovative because: (1) it will be the *first* trial to integrate modern technological tools, such as activity trackers to improve adherence to life style interventions aimed at preventing PTS. Although there are many ways to increase physical activity in children, my goal is to use a simple, user-friendly tool that will appeal to children across a broad age range; (2) activity/exercise as a therapeutic modality in children with DVT has not been previously studied; (3) there have been no previous randomized trials of PTS prevention or treatment in children; and (4) trial outcomes include patient reported outcomes (i.e. QoL) and laboratory based biomarkers.

PRIMARY AIM:

To demonstrate the feasibility and potential effectiveness of a personal “fitness tracker” to improve adherence to an activity regimen following an initial DVT in children.

[figure not shown]
Hypothesis: The intervention of using a fitness tracker to adhere to an activity regimen will be acceptable, and effective in improving adherence

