Clinical information will be collected from each patient's electronic medical record at all visits while on study. This information will include the following: name, gender, race, ethnicity, date of birth, current medications, social history, patient medical and hospitalization history; family history, physical exam and laboratory results. Additional information to be collected from self reported diaries include adherence data and adverse reaction data. Returned diaries will be maintained in a research binder, while medical history, lab results, and medications will be recorded in the electronic medical record and then on electronic Case Report Forms (eCRF). Contact phone numbers for parents and relatives will be collected for the interim visit phone calls.

b. DATA MANAGEMENT

The eCRF will be housed in UT Southwestern REDCap. REDCap is a self-managed, secure, web-based data support system. The data is backed up offsite nightly and hosted in a secure environment maintained by Information Resources. This password protected study database will include a subject's personal identifiers and all Protected Health Information (PHI) such as medical history. All personnel who will be accessing the data will be trained in REDCap and have individual user ID and passwords. Subjects will have a study ID number that will be utilized in lieu of personally identifiable information for all research data provided to statisticians.

c. STATISTICAL ANALYSES

The following will be calculated: the proportion of screened patients who fully met trial eligibility criteria, the proportion of eligible patients who consented to participate, the proportion in the physical activity/ Fitbit group who adhered to prescribed activity, and the proportion of randomized patients who completed the trial (in total, and by allocated intervention). The feasibility outcomes will be reported descriptively

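### Harm data are collected, but no planned analysis counts harms by arm and the definition of a successful pilot does not reflect them

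*Combined protocol and SAP*

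**What the plan says.** **Success rule.** Section VII (Outcomes and Power Calculations, Analyses): "We will consider the trial *successful* if the following criteria are met". The thresholds are eligibility at least 30%, consent at least 30%, loss to follow-up below 20%, compliance at least 60% and completion at least 80%. Table 2 lists only feasibility indicators.

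**Planned analyses.** The same paragraph states: "All analyses will therefore be descriptive and will be performed once, at the end of the trial". Under Data Collection, Management and Analysis, item c begins: "The following will be calculated: the proportion of screened patients who fully met trial eligibility criteria". It goes on to consent, adherence and completion, then to biomarkers, QoL, self-reported activity and PTS, with stocking use described. The clinical comparison is made "using an intent-to-treat analysis that includes all participants with data at baseline and 6 months".

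**Harm data.** Section V (Modifications, Risks) lists skin reactions to the tracker and activity-related injuries or falls. Item a of the data section says: "Additional information to be collected from self reported diaries include adherence data and adverse reaction data". Returned diaries go to a binder. The sentence on the eCRF names medical history, laboratory results and medications.

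**Nearest related provision.** The Analyses paragraph also says: "Reasons for non-eligibility, lack of consent, dropout and lack of compliance will be documented". Dropout is to be described in total and by arm.

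**The concern.** The Background asserts that an activity regimen "is unlikely to be harmful, maybe of benefit and needs further study", and that "a pilot study to establish feasibility of this approach is required before proceeding to a fully powered, definitive trial". A pilot that precedes a larger trial in children, some of them still on anticoagulants, would be expected to report what happened to them. Followed as written, this one can be called successful with no by-arm count of injuries, bleeding, new thrombosis or skin reactions.

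Two features make that hard to repair afterwards. The Fitbit arm is telephoned weekly and controls monthly (Table 1; Control arm section), so events mentioned without prompting would surface more often in the Fitbit arm even if true rates were equal. And the clinical comparison needs data at baseline and 6 months, so a child injured and withdrawn before Visit 2 is absent from the QoL and biomarker results. A question not asked alike in both arms during follow-up cannot be recovered at analysis.

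**Working it through.** **Inputs.** 44 children, 22 per arm (Sample size calculation; 1:1 allocation). Loss below 20%, completion at least 80%, compliance at least 60% of those given the prescription (Analyses). The documents give no harm rates and no figure of their own on this point, so there is none to reproduce.

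**1. What each existing route covers**

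| Route | Covers | Leaves open |
|---|---|---|
| Reasons for dropout and non-compliance; dropout by arm | Children who leave or miss the step goal | Harmed children who stay and comply; no link to the success rule |
| Medication log (Appendix 3) | Bleeding | Rivaroxaban users only |
| Stocking log (Appendix 4), both arms | Discomfort, pain, colour change, ulcers | Falls, other injuries, bleeding |
| Activity questionnaire (Appendix 5) | Leg pain or swelling, chest pain, breathing trouble, other reasons for less activity | Not listed as a harm count |
| PTS scales, physical QoL, D-dimer, compared by arm | Limb worsening, general decline | Discrete events |
| Skin monitoring (section VI, item c) | Individual care | No tabulation |

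No row yields a planned count of harms by arm.

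**2. How many harm withdrawals the thresholds allow**

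*Criteria read on the total.* Find the largest k with k/44 < 0.20 and (44 − k)/44 ≥ 0.80.
- k = 8: 8/44 = 18.2% lost, 36/44 = 81.8% complete. Passes.
- k = 9: 9/44 = 20.5% lost, 35/44 = 79.5% complete. Fails.
- Compliance: 14/22 = 63.6% passes; 13/22 = 59.1% fails.

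If all 8 are Fitbit children, 22 − 8 = 14 remain and every one must comply. Each control dropout lowers the maximum by one, so 4 control dropouts bring it to 4. If the 8 leave before the week-4 prescription, the compliance denominator is 14 and 9 compliers suffice (9/14 = 64.3%).

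*Criteria read by arm.*
- 4/22 = 18.2% lost, 18/22 = 81.8% complete. Passes.
- 5/22 = 22.7% lost. Fails.
- Of the 18 who remain, 14 must comply.

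The text describes dropout both ways and does not say which reading the threshold takes. The range is therefore 4 to 8 of 22 (18% to 36%). Two-sided Fisher p against 0 of 22 controls is 0.108 for 4 and 0.0036 for 8.

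**3. How extreme the upper end is.** If each of the 14 complies independently with assumed probability 0.7, 0.8 or 0.9, all 14 do so with probability 0.7^14 = 0.7%, 0.8^14 = 4.4% or 0.9^14 = 22.9%. Eight is a limiting case.

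**4. What a count in 22 children can show.** P(at least one event) = 1 − (1 − p)^22, which is 36%, 68% and 90% at assumed true rates of 2%, 5% and 10%. With no events, the one-sided 95% upper limit is 1 − 0.05^(1/22) = 12.7%; the upper end of a two-sided exact 95% interval is 1 − 0.025^(1/22) = 15.4%.

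**The case against.** The strongest reply is that this is a feasibility pilot, its criteria are feasibility criteria, and the plan already exposes the harm that matters most. An imbalance of 8 against 0 withdrawals would appear in the by-arm dropout description, with reasons on file. That stands. A reader might infer from the threshold arithmetic that the plan would conceal such an imbalance; it would not. What it lacks is any link from that imbalance to the success statement, and any count of harmed children who stay.

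It can also be said that success would often fail under heavy harm, because injured children miss step goals. That stands in part. Assume 20% harm withdrawal in the Fitbit arm, 5–10% other dropout in each arm and 80% compliance among those who stay. On the total reading, the loss, completion and compliance criteria are then all met with probability 29–47%. The rule therefore does respond to harm, but indirectly and without identifying it.

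It is tempting to add that injuries and falls have no prompt on any form. The documents do not establish this: the log tables are not reproduced in the available text, and the diaries are said to collect adverse-reaction data.

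Nor do the documents support reading the success rule as authority to start the larger trial. They say the pilot must come first, not that meeting the criteria is enough.

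**Conclusion.** The point holds as a reporting gap. Adverse-reaction data are collected and risks are named, but no planned analysis counts harms by arm and none of the five success criteria reflects harm. The written thresholds tolerate between 4 and 8 harm withdrawals among 22 Fitbit children; the upper figure needs no other dropouts in either arm and, with 22 as the compliance denominator, full compliance by the other 14. Harms without withdrawal have no direct limit. The main residual gap is the uncounted child who is harmed and stays, together with unequal contact between arms.

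This does not show that the regimen is unsafe, that clinical monitoring is inadequate, or that a mid-trial harms review is needed. The feasibility proportions are unaffected. The remedy is a cheap improvement, not a condition for the trial's validity.

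**What to change.** 1. Ask one identical harm question of both arms at Visits 2 and 3, or at withdrawal, covering the period since randomisation or the last visit. Record the answer on the eCRF and check it against the medical record.
2. Add one descriptive end-of-trial table for all randomised children, by arm, giving n (%) with exact 95% CI for: injury or fall leading to medical care; bleeding leading to care or a change of anticoagulant; new or recurrent DVT or PE; and, in the Fitbit arm, tracker skin reactions.
3. Report the table beside the success statement, and word that statement as feasibility only.

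No numerical harm criterion is proposed. With 22 per arm any cut-off would be arbitrary; for example, allowing the Fitbit arm no more than 2 extra affected children would pass 56–62% of the time at a true excess of 10 percentage points (assumed control rates 0–10%).

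The cost is one eCRF question, a few event definitions, one table and a little chart review, mainly for children who withdraw. No visit, committee or interim analysis is added, and the single end-of-trial descriptive analysis is kept. The downside is imprecision: 0 of 22 still allows a true rate up to 13% (one-sided 95%), so the table can describe harms but cannot show safety.
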